## **OBJECTIVES:**

### **1.0 Research Aims:**

#### **1. Research Question:**

Is there a detectable difference upper extremity strength as measured with dynamometry after cervical epidural steroid injections when lidocaine is used instead of saline as a steroid diluent in patients with cervical radiculitis?

#### **2. Null Hypothesis:**

There is no difference in upper extremity strength when lidocaine is used as a steroid diluent instead of saline for cervical epidural steroid injections.

## **BACKGROUND:**

### **Literature:**

Cervical radicular pain is a common problem that is often treated by epidural steroid injection (1). While clinical practice guidelines do not specifically recommend or discourage the use of local anesthetic in the epidural injectate (2), the majority of the published literature on clinical outcomes of cervical epidural steroid injection includes the use of lidocaine in the epidural injectate (3-11). Consequently, many practitioners elect to use local anesthetic in the epidural injectate in order to provide immediate pain relief to patients in cases of exquisitely painful radicular symptoms. Local anesthetic may also be used in such cases to gain additional clinical information regarding a patient's analgesic response, which may help pinpoint a precise anatomic source of pain when the clinical presentation and pain generator is not clear.

Local anesthetic injection into the epidural space has the potential to cause transient weakness of the upper extremities. High doses of local anesthetic in the cervical epidural space (12) and inappropriately placed low-dose local anesthetic in the subdural space or subarachnoid space (13,14) are known to cause motor weakness.

Appropriately placed, low-dose local anesthetic injected into the epidural space via a transforaminal approach, in close proximity to the exiting spinal nerve root, causes motor block in a small proportion of patients (15). However, the effect of low-dose injection of local anesthetic in the cervical interlaminar epidural space on objective upper extremity strength has not been well characterized in the published literature.

This proposition affects post-procedure instructions, as even mild weakness may pose a hazard during performance manual activities that require the upper extremity/extremities such as using a handrail or cane handle for support.

Dynamometry is an established method for assessing muscle strength and motor neuron function with high reliability, and has been used to objectively assess changes in upper extremity strength and has been validated in several patient populations (16-22).

This study aims to determine whether a standard dose of 2 mL 1% lidocaine vs 2mL of saline included as a steroid diluent in a C7-T1 cervical interlaminar epidural steroid injection (CESI) causes an objective change in strength as measured by dynamometry.

We hypothesize that CESI with lidocaine will cause an objective transient decrease in upper extremity strength, consistent with the expected duration of this local anesthetic.

**Significance:** Cervical radiculitis is a relatively common pain syndrome and is often treated with cervical epidural steroid injection (CESI) when conservative treatments (oral analgesics, physical therapy and activity modification for example) have failed to provide relief of symptoms. There are no universal clinical practice guidelines for the use of or type of diluents when CESI are performed.

Interlaminar CESI may be performed with or without the use of local anesthetics. CESI without the benefit of local anesthetic as a steroid diluent will not provide immediate relief of pain in patients with excruciating radicular symptoms, and also limits clinical information gleaned from the immediate analgesic response. Finally, the lack of immediate pain relief following spine interventions for chronic pain management may decrease patient satisfaction (23).

By evaluating the effects of local anesthetic as a diluent during interlaminar CESI, we will provide information about the potential for objective motor weakness with this commonly performed pain management procedure.

### **INCLUSION AND EXCLUSION CRITERIA:**

Patients who plan to undergo CESI for treatment of cervical radiculitis or the control group (no CESI) will be screened for eligibility by authorized research personnel during their visit to the Northwestern Anesthesiology Pain Medicine Center, [name], Lavin Pavilion.

#### **CESI Group**

##### **Inclusion criteria:**

All patients ages 18 years or older who will undergo CESI for treatment of cervical radiculitis.

##### **Exclusion criteria:**

Subject refusal

Subject unwilling to provide written consent

History of a hypersensitivity to amide local anesthetics

Any medical contraindication to CESI

Inability of the subject to communicate in English with research personnel

Inability of the subject to perform handgrip or arm strength testing

Cervical spinal cord lesions

Cerebrovascular, demyelinating or other neuromuscular muscular disease

Subject request for or requirement of intravenous conscious sedation for the injection procedure

Pregnancy  
Breast feeding

**Non CESI Group (control)**

**Inclusion Criteria:**

All patients ages 18 years or older who will undergo trigger point injections (TPI)

TPI include: Occipital facet or cervical facet injection

**Exclusion Criteria:**

Subject refusal

Subject unwilling to provide written consent

Pregnant

Breastfeeding

History of a hypersensitivity to amide local anesthetics

Inability of the subject to communicate in English with research personnel

Inability of the subject to perform handgrip or arm strength testing

Cervical spinal cord lesions

Cerebrovascular, demyelinating or other neuromuscular muscular disease

**STUDY-WIDE NUMBER OF PARTICIPANTS:**

Sample Size Calculation

Group 1: n = 60 (CESI with Lidocaine Diluent)

Group 2: n = 60 (CESI with Saline Diluent)

Group 3: n = 20 (no CESI, control group)

A power analysis was performed based upon previous observations of changes in UE strength (24,25) using Fisher's Exact Test. Sample sizes of 52 in each of the two treatment groups will achieve > 80% power to detect a group different in proportions, assuming 20% of patients in the Lidocaine group will demonstrate a motor deficit after the CESI and those in the Saline group will demonstrate no difference in motor strength after the CESI, and further assuming a 2% measurement error with the strength testing method described. The alpha level of this test statistic is set at 0.05, but the significance level actually achieved by this study design is 0.0004. To allow for drop outs, a total of 130 subjects will be enrolled in group 1 and 2. Group 3 will enroll a convenience sample of 20 control subjects based on available patients. Total of 150 subjects for the study will be enrolled.

**Statistical analysis:** The primary outcome (UE strength by dynamometry will be compared between the lidocaine and control group using Fisher's Exact Test. Secondary outcomes will be compared using the Mann-Whitney test for continuous data and a chi-squared statistic. A P <0.05 will be required to reject the null hypothesis.

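### The stated achieved significance level of 0.0004 holds only if both arms have a 2% deficit rate; it should be restated, and an unconditional exact test would give somewhat more power at the same alpha and sample size

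*Combined protocol and SAP*

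**What the plan says.** The sample size calculation, under STUDY-WIDE NUMBER OF PARTICIPANTS, is based on Fisher's exact test. It states that "Sample sizes of 52 in each of the two treatment groups will achieve > 80% power". For the lidocaine arm the calculation proceeds by "assuming 20% of patients in the Lidocaine group will demonstrate a motor deficit after the CESI". For the saline arm it expects no change in strength at all, and it allows for imprecise dynamometry by "further assuming a 2% measurement error with the strength testing method described". On the error rate it says "The alpha level of this test statistic is set at 0.05", and then "but the significance level actually achieved by this study design is 0.0004". No condition is attached to the 0.0004.

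The Statistical analysis paragraph of the same section keeps Fisher's exact test for the primary outcome and requires P below 0.05 for rejection. No other exact test is mentioned. The groups are listed at 60 each in this section and under NUMBER OF LOCAL PARTICIPANTS. The allowance for dropout brings enrolment in groups 1 and 2 to 130, or 65 per arm.

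**The concern.** With binary data, the chance that Fisher's test rejects a true null depends on the rate that the two arms share. The level of the test is the largest such chance over all common rates. The Null Hypothesis section says only that the arms do not differ; it does not fix the common rate at 2%. A single figure presented as the level of the design therefore needs either to be that maximum or to carry the condition under which it holds.

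Two things are at stake. A reader who takes 0.0004 at face value has too favourable a picture of the false-positive probability. And so small a value shows how conservative Fisher's test is when deficits are rare, which raises the question of whether power is being given up at the chosen alpha.

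**Working it through.** **Inputs.** From the sample size section: 52 per arm; 20% deficits with lidocaine; no true deficits with saline; 2% measurement error; alpha 0.05; Fisher's exact test. Two inputs are inferred, not stated: the test is two-sided, and the 2% error acts as the observed deficit rate in the saline arm.

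**Formula.** Let X and Y be the numbers with a deficit, independent binomials with n per arm and rates p1 and p2. Let R be the set of tables (x, y) with two-sided Fisher P ≤ 0.05. Then

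Pr(reject) = Σ over (x, y) in R of C(n,x) p1^x (1−p1)^(n−x) · C(n,y) p2^y (1−p2)^(n−y).

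Power uses p1 = 0.20 and p2 = 0.02. The null rejection probability uses p1 = p2 = p, and the level is its maximum over p. All 53 × 53 tables were enumerated at n = 52.

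**Step 1: reproduce the plan.**
- Power at 0.20 v 0.02: 0.803 at n = 52 and 0.791 at n = 51. This matches the claim of more than 80% and the choice of 52.
- Null rejection probability at p = 0.02: 0.00021 in each tail, 2 × 0.00021 = 0.00042. This matches 0.0004.
- Alternatives that do not give both figures: one-sided Fisher (power 0.897, null 0.0014); saline rate 0 (0.963, 0); saline rate 1% (0.889, 0.00002).

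Both printed figures are therefore explained by a two-sided test with a 2% saline rate.

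**Step 2: vary the common rate at n = 52, Fisher.**

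| Common rate | Null rejection probability |
|---|---|
| 2% | 0.00042 |
| 5% | 0.0079 |
| 10% | 0.0187 |
| 11% (mean of 20% and 2%) | 0.0201 |
| 15% | 0.0250 |
| 20% | 0.0291 |
| 50% (maximum) | 0.0390 |

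The maximum is about 0.035 at 60 and at 65 per arm. At a 2% common rate the value is 0.0008 at 60 and 0.0011 at 65, so even with its condition attached 0.0004 belongs to 52 per arm only.

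**Step 3: an exact test that uses more of the 0.05.** Boschloo's test orders tables by the Fisher P value and raises the cut-off as far as the maximum null rejection probability allows. At n = 52 the cut-off becomes 0.0725 and the maximum size is 0.0495; the next possible cut-off would give 0.0516. The test rejects whenever Fisher's does and also takes in tables such as 5 v 0 (Fisher P 0.057), 7 v 1 (0.060) and 9 v 2 (0.052).

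| n per arm | Fisher power | Boschloo power | Gain (points) |
|---|---|---|---|
| 52 | 80.3% | 87.5% | 7.2 |
| 60 | 87.8% | 91.5% | 3.8 (from unrounded values) |
| 65 | 91.1% | 93.8% | 2.7 |

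Power is at 20% v 2%, two-sided 0.05. Boschloo's test first reaches 80% at 45 per arm (80.7%), where Fisher's has 73.4%.

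**The case against.** The strongest reply is that 0.0004 is a correct number under the plan's own 2% assumption, that the same sentence sets alpha at 0.05, and that the analysis paragraph makes P<0.05 the decision rule. All of that stands. What is missing is the condition.

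A reader might infer several stronger things that the documents do not support:
- *That the calculation is in error.* It is not; both printed figures reproduce.
- *That the false-positive risk is out of control, or about 100 times what was planned.* The ratio 0.0390/0.00042 is about 93, but it needs a 50% common rate, far outside the plan's 2% to 20%. At 20% the ratio is 0.0291/0.00042, about 69. In every case the level stays below 0.05.
- *That Fisher's test is wrong.* It is valid, it agrees with the power calculation, and it meets the stated target with 80.3%.
- *That seven points of power are lost in the trial as planned.* That is the gain at 52 per arm, the size used in the calculation. At 60 or 65 it is 3.8 or 2.7 points.
- *That Boschloo's test removes the conservatism.* At a 2% common rate its rejection probability at n = 52 is 0.0027, still far below 0.05. In the worst case Fisher's leaves only 0.05 − 0.039 = 0.011 unused.

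It is also fair to object that STUDY ENDPOINTS defines the primary outcome as a change in strength and gives no threshold for a motor deficit. Until a threshold exists, the 20% and 2% rates, and so the size of the gain, remain hypothetical. That limits the power comparison. It does not rescue the 0.0004 sentence, which already treats the outcome as binary.

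**Conclusion.** The point holds in two parts of different weight.

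First, the 0.0004 statement is misleading as worded. It gives the rejection probability at a 2% rate in both arms as if it were a property of the design. For common rates from 5% to 20% the probability is 0.008 to 0.029 at 52 per arm, with a maximum of 0.039. This is a reporting fault: no conclusion of the trial is endangered and the decision rule does not change.

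Second, the choice of Fisher's test costs some power at the same alpha and n: 7.2 points at 52 per arm and about 3 to 4 points at the planned 60 to 65. This is an opportunity, not an error.

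Both parts rest on the two inferred inputs (two-sided test, 2% saline rate) and on a comparison of lidocaine with saline. The power figures also need the primary outcome to be analysed as a binary motor deficit, as the sample size calculation does.

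**What to change.** Replace the 0.0004 sentence with, for example:

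> The test is held at two-sided 0.05. At 52 per group, the rejection probability of Fisher's test is 0.0004 if both groups have a 2% rate, and at most 0.039 for any common rate (about 0.035 at 60 or 65 per group).

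This costs nothing and changes neither the sample size nor the conduct of the trial.

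As an optional improvement, before unblinding, name Boschloo's unconditional exact test (two-sided 0.05) as the primary comparison of the two randomised arms, and keep Fisher's exact test as a sensitivity analysis. The cost is one further sentence and a test that readers know less well; the type I error stays at or below 0.05. The sentence should also say that the comparison is of a binary motor deficit, so that the test matches the outcome on which the power rests.

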**STUDY-WIDE RECRUITMENT METHODS: N/A**

## **MULTI-SITE RESEARCH: N/A**

### **STUDY TIMELINES:**

Each enrolled subject will receive a follow up telephone call 24 hours and one week after the procedure. The anticipated duration for study enrollment is 6 months.

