### **STUDY ENDPOINTS:**

#### **Primary outcome:**

Change in upper extremity strength defined by dynamometry measurements for each individual in each treatment group before and 30 minutes after the procedure (CESI or no CESI).

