### **PROCEDURES INVOLVED:**

#### **Study design:**

Prospective, randomized, controlled, double blinded trial in patients undergoing CESI for symptoms of cervical radiculitis.

**Group #1:** Interlaminar cervical ESI at the C7-T1 level with triamcinolone 80 mg + 2 mL 1% lidocaine (total volume 4 cc).

**Group #2:** Interlaminar cervical ESI at the C7-T1 level with triamcinolone 80 mg + 2 mL preservative saline (total volume 4 cc).

**Group #3:** Control group (No CESI) cervical or occipital facet injection

Adults who are eligible to have a CESI for treatment of cervical radiculitis at the Northwestern Anesthesiology Pain Medicine Center will be approached by authorized research personnel prior to a patient's CESI is performed and will obtain informed consent from patients who agree to participate.

A pre-procedure NRS pain score and presence of subjective or objective symptoms of UE weakness will be recorded by a blinded authorized study team member. Bilateral handgrip, wrist extension, elbow flexion, and elbow extension strength (myotomes C5-T1) will be measured prior to the injection procedure using a handheld JAMAR® PLUS+ digital dynamometer (Sammons Preston, Bolingbrook, IL) for hand grip strength and a push/pull handheld hydraulic dynamometer (Balego and Associates Inc., St. Paul, MN) for arm strength assessment. Three baseline strength measurements will be recorded for each strength test. Measurements will be taken prior to and 30 minutes following the

injection procedure. Participants will also be queried with the Upper Extremity Functional Index (UEFI) before the injection procedure and again 1 day and 1 week after the procedure (administered via telephone).

Group 1 and 2 participants will be randomized to treatment group based on a random computer-generated schedule (<https://www.randomizer.org>) and will be blinded to the group to which they are assigned. Blinding will not occur with Group 3. Providers will not be blinded to randomization; blinded research personnel will collect all outcome measures in this study.

All standard Pain Center procedures for CESIs will be followed (standard practice) including time out, skin prep, hemodynamic monitoring, image guidance, post-injection instruction etc.

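### Group sizes of 60/60/20 do not add up to the stated enrolment of 130 and 150, and the primary outcome (a change in strength over eight tests) has no rule giving the yes/no result per patient that Fisher's exact test needs

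*Combined protocol and SAP*

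**What the plan says.** **Numbers.** In the combined protocol and SAP, the section Study-wide number of participants opens with a list: "Group 1: n = 60 (CESI with Lidocaine Diluent"), then 60 for saline and 20 for the non-CESI control group. Number of local participants repeats 60/60/20. The text below the first list requires 52 per treatment arm, then says "To allow for drop outs, a total of 130 subjects will be enrolled in group 1 and 2" and "Total of 150 subjects for the study will be enrolled". No drop-out rate is given. The trial has one site: "MULTI-SITE RESEARCH: N/A".

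**Power basis.** The calculation is for Fisher's exact test. It assumes a motor deficit in 20% of lidocaine patients and no change in strength under saline, "and further assuming a 2% measurement error with the strength testing method described". It reports more than 80% power, a nominal alpha of 0.05 and an achieved level of 0.0004.

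**Endpoint and analysis.** Study endpoints defines the primary outcome as "Change in upper extremity strength defined by dynamometry measurements for each individual in each treatment group before and 30 minutes after the procedure". Procedures involved states that "Bilateral handgrip, wrist extension, elbow flexion, and elbow extension strength (myotomes C5-T1) will be measured prior to the injection procedure", with three baseline readings per test. Under Statistical analysis, the primary outcome "will be compared between the lidocaine and control group using Fisher's Exact Test".

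**The concern.** There are two separate faults in the text that fixes the size and the primary analysis of the trial.

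1. The listed group sizes and the enrolment text differ by 10 patients. At a single site the local count cannot be a subset of a larger total. Without a drop-out rate, the reader cannot tell which figure was derived from the 104 evaluable patients required.

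2. Fisher's exact test needs one category per patient. The stated outcome is a change in strength, measured by four movements on two sides. No section gives a strength-loss cut-off, says which movements or sides count, says how repeat readings are summarised, or says how eight results become one. The primary test therefore cannot be run from the plan as written. The rule that creates the primary result, and with it the P value, is not required to be fixed before the data are seen.

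The comparator is also unclear. The analysis sentence sets lidocaine against the control group, a label the protocol gives to the non-randomised Group 3, while the power calculation compares lidocaine with saline.

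**Working it through.** **Inputs.** From Study-wide number of participants: 60/60/20 listed; 130 and 150 enrolled; 52 per arm required; lidocaine deficit 20%; saline no change; 2% measurement error; alpha 0.05; achieved level 0.0004. Sidedness is not stated.

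**Step 1: reproduce the plan's power.** Exact power of the two-sided Fisher test is the sum, over all pairs (a, b) with P ≤ 0.05, of Bin(a; n, p1) × Bin(b; n, p2). The achieved level is the same sum with both rates set to the saline rate.

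| n per arm | p1 | p2 | Power | Achieved level |
|---|---|---|---|---|
| 52 | 0.20 | 0.02 | 80.3% | 0.00042 |
| 52 | 0.20 | 0.01 | 88.9% | 0.00002 |
| 52 | 0.20 | 0 | 96.3% | 0 |

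The first row matches both stated figures, and 52 is the smallest n per arm that reaches 80% there. The one-sided version at 2% gives 89.7% and 0.0014, which does not match. Of the readings tried, only the two-sided test with 2% as the saline event rate fits. The calculation is therefore sound, and its 2% is a share of patients, not an amount of strength loss.

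**Step 2: enrolment.**
- List: 60 + 60 = 120; 120 + 20 = 140.
- Text: 130 + 20 = 150.
- Required evaluable: 2 × 52 = 104.
- Loss allowed by 120: 1 − 104/120 = 13.3%.
- Loss allowed by 130: 1 − 104/130 = 20.0%; equivalently 104/0.80 = 130 exactly.

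**Step 3: what the difference is worth, at 20% v 2%.**

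| Enrolled (two arms) | Loss | Evaluable per arm | Power |
|---|---|---|---|
| 120 | 0% | 60 | 87.8% |
| 130 | 0% | 65 | 91.1% |
| 120 | 20% | 48 | 75.3% |
| 130 | 20% | 52 | 80.3% |

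The 20% loss is the rate implied by 130, not one the plan states.

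**Step 4: endpoint against test.** Four movements × two sides = 8 tests per patient at each time point, with three baseline readings each. The test needs 1 yes/no per patient. No section supplies the step from 8 to 1.

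**Step 5: how power moves with the saline rate that a rule produces, 52 per arm.** Scenario A takes 20% as the rate observed under lidocaine. Scenario B takes 20% as the true rate and lets false deficits occur in both arms at rate s, so that lidocaine = 1 − 0.8(1 − s), which is 21.6%, 22.4% and 24.0% for the three rows.

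| Saline rate s | A | B |
|---|---|---|
| 2% | 80.3% | 85.9% |
| 3% | 71.2% | 81.3% |
| 5% | 53.4% | 73.2% |

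The 3% and 5% rates are illustrations; the documents do not say what rate any rule would give.

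**The case against.** **On the numbers.** The protocol prints neither 120 nor 140; they are sums of the listed sizes. The only statements of how many will be enrolled are 130 and 150, and 130 is exactly what 20% drop-out from 104 would give. A reader might infer that the protocol sets two rival recruitment targets; that goes too far, because the text points to 130. One could also read 60 per arm as an evaluable target, but the stated requirement is 52, and the section on local participants lists 60/60/20 without qualification. Consent and the 30-minute measurement both fall on the procedure day, so loss for the primary outcome may be small. What stands is an inconsistency that needs correcting, with a modest effect.

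**On power.** A reader might infer that the sample size is wrong, or that 80% power holds only while the saline rate stays at or below about 2%. Neither is supported. The calculation reproduces. A limit near 2% only restates the plan's own assumption, since 52 is the smallest n reaching 80% there, and under scenario B power is still 81.3% at 3%. A different rule would also change how many true deficits are detected under lidocaine, which neither scenario models. Nor do the documents support a power figure for a rule counting any one of eight positive tests: that would need a per-test error rate and a correlation between tests, and neither is given.

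**On choosing the rule late.** Blinded personnel collect all outcomes, the section Drugs or devices says the research team is blinded, and the allocation becomes known to that team after completion. This lowers the risk of a rule chosen to favour a result. It does not remove it: providers are not blinded, and nothing requires the rule to be fixed before unblinding.

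**Conclusion.** The point holds in two parts of unequal weight.

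The endpoint gap is the main one. The primary outcome as defined and the primary test as named do not fit together, and nothing in the document links them. The 2% cannot serve as the missing threshold, because the plan's own power and achieved level reproduce with it as a per-patient saline deficit rate. At 52 per arm, moving that rate from 2% to 5% lowers power from 80.3% to 53.4% under scenario A, or from 85.9% to 73.2% under scenario B. This shows that the power depends on a rule not yet written; it does not show that the trial is underpowered.

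The enrolment mismatch is a consistency fault of 10 patients. With little loss, either figure keeps power above 80% at the plan's assumptions. The choice matters only if loss exceeds the 13.3% that 120 allows. All figures assume a two-sided Fisher test at 0.05 and equal arms.

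**What to change.** 1. **Enrolment.** Make Study-wide number of participants and Number of local participants agree. The text's figures fit 65 + 65 + 20 = 150, with a 20% drop-out rate stated. If 60 per arm is kept as the enrolment, delete 130 and 150 and state that 120 allows 13.3% loss from the 104 required.

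2. **Primary outcome.** Before unblinding, do one of the following:
   - set one patient-level binary outcome, naming the movements and sides that count, the strength-loss threshold used for the analysis, and how repeat readings and tests are combined, for a single Fisher test; or
   - make one patient-level continuous change score primary, with a test that suits it.

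3. **Comparator.** State that the primary test compares lidocaine (Group 1) with saline (Group 2), and drop the term control group from that sentence.

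4. **Power.** Describe the 2% as the assumed per-patient deficit rate under saline, say whether false deficits are also expected under lidocaine, and restate power for the chosen outcome.

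The cost is protocol wording. The downside is that the restated power may be less favourable than the present figure, and whether 120 or 130 is then enough depends on the outcome chosen.

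### The primary-analysis sentence names the control group, the protocol's label for the 20 non-randomised Group 3 patients, as comparator, while the hypothesis and power calculation use saline

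*Combined protocol and SAP*

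**What the plan says.** The primary test is defined in one sentence, in the Statistical analysis paragraph under STUDY-WIDE NUMBER OF PARTICIPANTS: "The primary outcome (UE strength by dynamometry will be compared between the lidocaine and control group using Fisher's Exact Test". The paragraph closes with "A P <0.05 will be required to reject the null hypothesis".

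The sample size list in the same section has "Group 3: n = 20 (no CESI, control group"), and the power paragraph adds "Group 3 will enroll a convenience sample of 20 control subjects based on available patients". The eligibility section and the study design list under PROCEDURES INVOLVED also attach the word control to the no-CESI group. Group 2 is identified by its number or by its saline diluent and is nowhere called the control group.

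The rest of the plan points to a different comparison. The Research Question asks about strength "when lidocaine is used instead of saline as a steroid diluent in patients with cervical radiculitis". The Null Hypothesis and the aim at the end of the Literature section make the same contrast. The power paragraph states "Sample sizes of 52 in each of the two treatment groups will achieve > 80% power" and assumes a 20% deficit rate with lidocaine, that "those in the Saline group will demonstrate no difference in motor strength after the CESI", and a 2% measurement error. It also reports that "the significance level actually achieved by this study design is 0.0004".

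**The concern.** The plan is powered for one comparison and names another in the only sentence that defines the primary test. If that sentence is followed as written:

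- The randomised comparison is lost, because the computer-generated schedule covers only Groups 1 and 2.
- Diluent is confounded with procedure, patient selection, steroid and local anesthetic. Group 3 has facet or trigger point injections, with intramuscular bupivacaine and methylprednisolone in place of epidural triamcinolone with lidocaine.
- The stated null hypothesis, lidocaine against saline, is not tested.
- The comparator has 20 patients instead of 60, so the stated power does not apply.

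The Primary outcome definition under STUDY ENDPOINTS covers CESI and no-CESI procedures alike, so Group 3 supplies primary-outcome data. No sentence says how those data enter the analysis. Two possible comparators with the same endpoint leave room to choose between them after the results are seen.

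**Working it through.** **Inputs.** From the power paragraph: lidocaine deficit rate 20%; no deficit with saline; 2% measurement error; alpha 0.05; 52 per arm. From the group list: 60, 60 and 20. The documents do not say whether the test is one- or two-sided; two-sided is assumed. They give no deficit rate for Group 3, so 0% and 2% are borrowed from the saline and measurement-error inputs.

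**Formula.** Power = Σᵢ Σⱼ Bin(i; n₁, p₁) × Bin(j; n₂, p₂) × 1[Fisher P(i, j) < 0.05], summed over every possible table. Setting p₁ = p₂ gives the size actually achieved.

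**Step 1: reproduce the plan's figures.** With n₁ = n₂ = 52, p₁ = 0.20 and p₂ = 0.02, power is 0.803, and 52 is the smallest number per arm that reaches 80%. With 2% in both arms the achieved size is 0.00042, which rounds to the stated 0.0004. By contrast, 60 v 20 with 2% in both arms has size 0.00481. A one-sided test at 52 v 52 gives 89.7% power and size 0.00136, so the two-sided assumption fits. The published calculation is therefore lidocaine v saline.

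**Step 2: power under each reading** (two-sided, lidocaine 20%).

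| Comparison | n₁ v n₂ | Comparator 0% | Comparator 2% |
|---|---|---|---|
| Group 1 v Group 2 | 52 v 52 | 96.3% | 80.3% |
| Group 1 v Group 2 | 60 v 60 | 98.8% | 87.8% |
| Group 1 v Group 2 | 65 v 65 | 99.4% | 91.1% |
| Group 1 v Group 3 | 52 v 20 | 47.2% | 33.8% |
| Group 1 v Group 3 | 60 v 20 | 55.1% | 39.0% |
| Group 1 v Group 3 | 65 v 20 | 54.9% | 39.0% |

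The 65 rows split the 130 planned enrolments equally. A one-sided test at 60 v 20 gives 78.7% (0%) and 58.3% (2%), so the literal reading stays below 80% in every variant tried.

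**Step 3: lidocaine deficits needed for significance, out of 60.**

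| Comparator result | Smallest significant count | P |
|---|---|---|
| 0/60 (Group 2) | 6 (10%) | 0.027 |
| 1/60 (Group 2) | 8 (13%) | 0.032 |
| 0/20 (Group 3) | 12 (20%) | 0.031 |
| 1/20 (Group 3) | 17 (28%) | 0.033 |

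**Step 4: effect on the conclusion.** The planned rate gives 0.20 × 60 = 12 deficits. Against one deficit among 60 saline patients, P = 0.002. Against one deficit among 20 Group 3 patients, P = 0.167. The same lidocaine result passes one test and fails the other.

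**The case against.** The strongest reply is that saline is plainly meant. The sentence directly follows a power paragraph for the same test that names the lidocaine and saline groups. Its paragraph ends by referring to the null hypothesis, which is lidocaine against saline. The design is described as a controlled trial in patients undergoing CESI, where the control could only be saline. On this view the 39.0% and 55.1% figures describe a test that probably nobody planned, and they rest on a borrowed Group 3 rate.

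Most of this stands. Intent is recoverable, and the power loss is what the literal sentence would cost, not an expected loss for the trial. It does not remove the inconsistency. Controlled is a general design term; as a group label, control always means Group 3. The power paragraph shows what was intended but does not define the test. The endpoint definition, by including no-CESI procedures, makes the literal reading less far-fetched.

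A smaller point also stands. The protocol says blinding will not occur with Group 3, but also that blinded personnel collect all outcome measures. It does not say whether the assessors of Group 3 are blinded, so the case against using Group 3 should not rest on unblinded assessment.

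**Conclusion.** The concern holds: the sentence is wrong as written and should be fixed. The reason is textual: the one sentence that defines the primary test uses Group 3's label, against the research question, null hypothesis, aim and power calculation. This is a correction to the analysis text, not a design failure.

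The size applies only if the sentence is followed literally: at 60 lidocaine patients, power falls from 87.8% to 39.0% (comparator rate 2%) or from 98.8% to 55.1% (0%). This assumes a two-sided test at 0.05, the plan's 20% lidocaine rate, and the same comparator rate in Group 2 and Group 3. The contradiction itself needs none of these assumptions.

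**What to change.** In the Statistical analysis paragraph, replace the words naming the two groups with: *between Group 1 (lidocaine diluent) and Group 2 (saline diluent)*. Add one sentence, referring to the Primary outcome definition, which includes no-CESI procedures: *Group 3 does not enter the primary test; its results are reported descriptively* (or *as a labelled secondary comparison*, as the sponsor chooses).

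The cost is one edited phrase and one added sentence, with no extra patients or data. The edit does not supply the yes/no deficit cut-off that Fisher's test needs and the Primary outcome section does not give. That is a separate matter.
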